After the planned preliminary interim of the Sentinel Cohort participants, a decision to discontinue the development of the mRNA COVID-19 vaccine was made. On September 27, 2021, all Investigators were informed to terminate further vaccinations and enrollment. All enrolled participants were to be unblinded to allow them to make their decision to receive an authorized COVID-19 vaccine. All clinical sites were to contact participants to inform them of the discontinuation of further study vaccinations, told what intervention they received and invited to come in for an unscheduled visit for counseling to answer any questions about the study, to discuss available options for receipt of an approved /authorized COVID vaccination, and were requested to provide unscheduled blood draw for serological assessment (UBXX). Participants were informed that additional D22 or D36 blood draws for serological assessment would be appreciated but are not mandatory. No protocol defined schedule visits or blood draws at timepoints later than D36 were required. Monitoring for SAEs, AESIs, medically attended AEs, and pregnancy and collection of influenza and COVID-19 vaccines were continued with safety calls. On March 15, 2022, after concurrence from regulatory authorities, Investigators were notified of the decision to end the study at the 6-month safety follow-up instead of 12-month follow-up.

This version 5.0 of SAP is updated for the final unblinded analysis. The sections of Trial Objectives and Trial Design and Plan are kept the same with the final protocol, but modifications are made in Section 4 and Section 5 for endpoint derivation, statistical methods, and populations used in analyses, to reflect the changes needed for the final analyses.

2 Trial Objectives

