4.4 Derived Endpoints: Calculation Methods

4.4.1 Safety

The main safety analysis will include all events or reactions with time of onset before the date of receiving a non-study authorized/approved COVID-19 vaccine and including only the corresponding safety data collected before the date of receiving a non-study authorized/approved COVID-19 vaccine. The endpoints derivations for safety analysis are detailed in the following sections. Conducting main analysis with data censored by the date of receiving a non-study authorized/approved COVID-19 vaccine will only be applied to some selected endpoints. Details on the conduct of the main safety analysis for those endpoints are provided in the following subsections. Other endpoints will be analyzed as usual. Events or reactions with time of onset on or after the date of receiving a non-study authorized/approved COVID-19 vaccine will be listed separately.

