5.1 Statistical Methods

Safety, immunogenicity, and efficacy analysis will be undertaken including those data collected before the date of receiving an authorized/approved COVID-19 vaccine. Those data collected on or after receiving an authorized/approved COVID-19 vaccine will be listed separately.

For those participants who did not receive an authorized/approved COVID-19 vaccine outside the study, immunogenicity data collected until the last scheduled/unscheduled study visit will be used for analysis. Rules about how to handle unscheduled visit are detailed in Table 5.2. Safety data collected until the last phone contact will be used for analysis if participants did not receive an authorized/approved COVID-19 vaccine outside the study

Safety analyses will be conducted based on two populations: *i*) participants in the Full Enrollment Cohort (Cohort 1 and 2) only, and *ii*) all participants in the Full Enrollment Cohort and Sentinel Cohort, if necessary. Immunogenicity analyses and efficacy analyses will be conducted based on the combined population (Full Enrollment Cohort + Sentinel Cohort) only, in which the same

dose-level group in Sentinel Cohort and Full Enrollment Cohort will be pooled. Subgroup analyses will be performed by age-group.

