5.1.1.2 Statistical Methods for Primary Safety Objective

The following safety parameters will be used for the evaluation of safety. Additional parameters may be displayed as appropriate.

Solicited Reactions

Number and percentage of participants with:

- Presence of solicited injection site reactions and systemic reactions occurring up to 7 days after injection
- Each solicited reaction according to time of onset, maximum intensity, and number of days of occurrence over the solicited period

Unsolicited Events and Reactions

Number and percentage of participants with:

- Any unsolicited immediate systemic event in the 30 minutes after injection
- Any unsolicited event and reaction (using the current MedDRA version) 21 days after injection
- Any unsolicited event/reaction according to time of onset, maximum intensity, and duration

SAEs

Number and percentage of participants with:

- Any SAE within 21 days after injection and throughout the entire study according to SOC and PT, seriousness, and outcome

AESIs

Number and percentage of participants with:

- Any AESI within 21 days after injection and throughout the entire study according to SOC and PT, seriousness, and outcome

MAAEs

Number and percentage of participants with:

- Presence of MAAEs within 21 days after injection and throughout the entire study

Laboratory tests

- Presence of out-of-range biological test results up to 8 days post-last dose (ie, up to D09 for Cohort 1 and up to D30 for Sentinel Cohort and Cohort 2)
- Summary of toxicity grade shift from baseline

For descriptive purposes, the statistics presented in [Table 5.1](#) will be produced for the above safety parameters for each intervention group and each age group. The same dose-level group in Sentinel Cohort and Cohort 2 will also be pooled for analysis.

Harm analysis

Harm analysis assessed based on split of COVID-19 case will be assessed based on Safety Analysis Set (SafAS) at the time of the final analysis. Participants will be analyzed according to the study intervention they received. For the assessment, all dose-level arms will be pooled, and all placebo arms will be pooled as well.

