The assessment for COVID-19 will be implemented separately using a one-sided conditional exact binomial test of $H_0: p \leq \text{“number of participants in the pooled mRNA vaccine arm”} / \text{“total number of participants”}$ versus $H_1: p > \text{“number of participants in the pooled mRNA vaccine arm”} / \text{“total number of participants”}$, where p is the binomial probability that a case participant is assigned to the pooled mRNA vaccine group conditional on the observed total number of cases. The test will be performed at the same pre-specified one-sided nominal/unadjusted alpha-level of 0.05 (unadjusted). The bounds for harm monitoring are computed under the null hypothesis that $VE=0\%$.

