5.7 Changes in the Conduct of the Trial or Planned Analyses

The content of the current SAP is based on protocol v3.0 and the following modifications.

When conducting the planned preliminary interim analysis, as the sensitivity of the rapid diagnostic test (RDT), used to assess seropositivity at screening, was low, an ad hoc analysis set "mFAS" was defined as a subset of the FAS that excludes participants with positive pseudovirus neutralization test results against SARS-CoV-2 D614G variant at baseline. In addition, due to 8 participants in the Sentinel Cohort with dosing errors related protocol deviations, immunogenicity analyses were performed using "mFAS" according to the study intervention participants actually received. The "mFAS" by injection group will also be used in the final analysis.

After the planned preliminary interim of the Sentinel Cohort participants, a decision to discontinue the development of the mRNA COVID-19 vaccine was made. On September 27, 2021, all Investigators were informed to terminate further vaccinations and enrollment. All

enrolled participants were to be unblinded to allow them to make their decision to receive an authorized COVID-19 vaccine. All clinical sites were to contact participants to inform them of the discontinuation of further study vaccinations, told what intervention they received and invited to come in for an unscheduled visit for counseling to answer any questions about the study, to discuss available options for receipt of an approved /authorized COVID vaccination, and were requested to provide unscheduled blood draw for serological assessment (UBXX). Participants were informed that additional D22 or D36 blood draws for serological assessment would be appreciated but are not mandatory. No protocol defined schedule visits or blood draws at timepoints later than D36 were required. Monitoring for SAEs, AESIs, medically attended AEs, and pregnancy and collection of influenza and COVID-19 vaccines were continued with safety calls. On March 15, 2022, after concurrence from regulatory authorities, Investigators were notified of the decision to end the study at the 6-month safety follow-up instead of 12-month follow-up.

As the further development of the mRNA COVID-19 vaccine was terminated and as mentioned above in [Section 5.4](#), interim analyses initially planned in the protocol will not be performed. The final analysis will be conducted in an unblinded manner.

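### The COVID-19 harm test takes the vaccine share of participants as its VE = 0% null; on a rate scale that holds only if mean time at risk is equal in the vaccine and placebo arms

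*SAP*

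**What the plan says.** SAP 5.1.1.2 (Harm analysis) pools all dose levels against all placebo recipients. It applies a one-sided exact binomial test at 0.05, conditional on the total number of cases. The null share is the "number of participants in the pooled mRNA vaccine arm" over the total number of participants. It adds: "The bounds for harm monitoring are computed under the null hypothesis that" VE is 0%. It does not say whether VE is a rate or a risk measure, gives no time at risk, and does not say which of the two endpoints in SAP 4.4.4 is a case.

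**Timing.** Protocol 9.5 planned the first harm look on data to D43 and had the SMT notified if the boundary was met. In SAP v5.0 the analysis "will be assessed based on Safety Analysis Set (SafAS) at the time of the final analysis". By then, SAP 1 records: "All enrolled participants were to be unblinded to allow them to make their decision to receive an authorized COVID-19 vaccine." SAP 5.7 adds that participants were to be "told what intervention they received".

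**Cut-off.** SAP 5.1 analyzes data from before an authorized vaccine and states: "Those data collected on or after receiving an authorized/approved COVID-19 vaccine will be listed separately." Participants who took no outside vaccine contribute safety data to their last phone contact. SAP 3.1 agrees with the vaccine cut-off. SAP 4.4.1 says that the censoring "will only be applied to some selected endpoints", with the others handled as usual.

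**Population.** SAP 5.1 foresees safety analyses on the Full Enrollment Cohort alone and on "all participants in the Full Enrollment Cohort and Sentinel Cohort, if necessary". SAP 5.2.2 limits the SafAS to randomized participants, whereas Protocol 9.3 says enrolled.

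**The concern.** A share of participants equals the expected share of cases under equal rates only when each arm contributes the same average time at risk. Over a short common window, such as the protocol's D43 look, that is a reasonable approximation. At the final analysis, follow-up ends at an outside vaccine or the last phone contact, and the choice of an outside vaccine was made knowing the allocation.

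If placebo recipients leave the risk set sooner, the test signals harm too often. If vaccine recipients leave sooner, it can miss harm. On a risk scale the share of participants is the VE = 0% null, but unequal follow-up would then confound the comparison.

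SAP 5.1.2.4 drops the vaccine-efficacy analysis. Apart from this test, what remains on COVID-19 cases is descriptive: numbers and percentages by group (SAP Table 5.1), and last antibody levels before infection among cases (SAP 5.1.3). This is therefore the only formal comparison of case splits left.

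**Working it through.** **Inputs from the documents.** Protocol Table 4.3: vaccine 2 × 3 × (20 + 24) = 264; placebo 2 × (10 + 12) = 44; total 308, which matches the stated target. Test: exact binomial, one-sided 0.05 (SAP 5.1.1.2).

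**Assumptions.** Mean time at risk by arm (Tv vaccine, Tp placebo) and the number of cases n. The documents give neither, nor the realised arm sizes; enrollment stopped early.

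**Formulas.**
- Plan's null: p0 = 264/308 = 0.8571.
- Critical count: smallest k with P(X ≥ k | n, p0) ≤ 0.05.
- True share of cases under equal, constant rates: p* = 264·Tv / (264·Tv + 44·Tp). This equals p0 only if Tv = Tp.
- Actual error: P(X ≥ k | n, p*).

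**Plan's null with equal time.** The critical counts are 20 of 20, 39 of 40 and 57 of 60, with errors 4.6%, 1.6% and 2.1%. The test holds its level.

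**Unequal time, plan's null kept.**

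| Assumption | p* | n = 20 | n = 40 | n = 60 |
|---|---|---|---|---|
| Equal time | 264/308 = 0.8571 | 4.6% | 1.6% | 2.1% |
| Placebo time 90% of vaccine | 264/303.6 = 0.8696 | 6.1% | 2.6% | 3.8% |
| Placebo time 75% of vaccine | 264/297 = 0.8889 | 9.5% | 5.4% | 8.8% |
| Vaccine time 80% of placebo | 211.2/255.2 = 0.8276 | 2.3% | 0.5% | 0.5% |

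At placebo 90%, the errors at 25, 30 and 50 cases are 3.0%, 1.5% and 3.3%. So that ratio exceeds 5% at 20 cases but not at 25, 30, 40, 50 or 60.

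**Fewest cases that can reject.** This is the smallest n with p0^n ≤ 0.05: 0.8571^20 = 0.046, while 0.8571^19 = 0.053. Below 20 cases the planned-split test cannot reject.

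**Person-time null, p* in place of p0, constant incidence, n = 60.** Placebo 75%: critical count 58, error 3.1%. Vaccine 80%: critical count 55, error 4.1%. The level is kept by construction. At 40 cases with placebo 75%, the person-time null gives 0.9% (critical count 40) against 5.4% for the plan's null.

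**If incidence changes after unblinding, n = 60.** Take 0.5 time units before unblinding in both arms. After it, one arm has 0.5 and the other 0.25, so the shorter arm's total is 75% of the longer. Let r be incidence after over before, from 0.5 to 3.
- Placebo shorter: plan's null 5.5% (r = 0.5) to 17% (r = 3); person-time null 1.8% to 6.9%.
- Vaccine shorter: plan's null 0.6% (r = 0.5) to 0.05% (r = 3); person-time null 5.1% to 0.7%.

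The person-time null is less sensitive here, but it is not exact. Time before unblinding is equal in both scenarios, so an analysis stopped there has the same null on either basis.

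**The case against.** **Unequal time is conjecture.** This stands as a limit. The documents open a route to it, through disclosure of allocation and free choice of an authorized vaccine, but report no difference and no direction. A reader might infer that placebo recipients left sooner and that the test therefore over-signals harm. The documents do not support that inference.

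**The cut-off is already given.** Largely right. A reader might infer from SAP 4.4.1 that the rule for cases is open. But SAP 5.1 and 3.1 give a general rule. The limiting sentence sits in the section on derived safety endpoints, whereas cases are defined separately in SAP 4.4.4. What remains is a wording gap: the harm test is filed under safety, and its section repeats neither rule.

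**A person-time null is not always nearer 5%.** Correct. At placebo 75% it gives 0.9% against 5.4% with 40 cases. If incidence halves after unblinding, it gives 1.8% against 5.5% with 60 cases. Its merit is that it keeps the level at or below 5% under constant incidence.

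**Sixty cases is many.** Also fair: it is about 19% of 308, in a trial whose enrollment stopped early and whose follow-up ended at six months. With few cases the choice of null has no practical effect.

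**The share of participants is right on a risk scale.** True, but the plan does not choose that scale or fix a common follow-up window.

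**Conclusion.** The point holds, as a minor one. The stated null matches VE = 0% on a rate scale only with equal mean time at risk and similar background incidence over that time. Moving the test to the final analysis, after unblinding, removes the assurance of equal time. Under assumed time ratios, constant incidence, the planned split and 60 cases, the error runs from 0.5% (vaccine time 80% of placebo time) through 2.1% (equal time) to 8.8% (placebo time 75% of vaccine time).

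The documents do not establish that the test's error was inflated in this trial. The consequence is limited: the test runs once, after vaccination ended, and SAP v5.0 attaches no action to it. The remaining interim analyses were dropped (SAP 5.4).

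**What to change.** In SAP 5.1.1.2:

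1. Define a case for this test as virologically-confirmed COVID-19-like illness. Set the null share to vaccine person-time over total person-time, with time at risk running from D01 to the first of case, authorized COVID-19 vaccine or last contact. Do not apply this time rule to serologically-confirmed infection. That endpoint needs a serum sample, and after D36 no scheduled draws were required while follow-up continued by safety calls.
2. State that the general rule in SAP 5.1 and 3.1 (data before an authorized vaccine) governs this test, so that the selected-endpoints wording in SAP 4.4.1 does not leave it open.
3. As a sensitivity analysis, repeat the test with follow-up stopped at individual unblinding, or at 27 September 2021 if individual dates were not recorded.
4. State that the test uses the randomized Full Enrollment Cohort, as SAP 5.2.2 and 5.2.4 read literally, because the Sentinel Cohort has no placebo group.

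**Cost.** SAP wording and one person-time derivation; receipt of COVID-19 vaccines continued to be collected. The sensitivity analysis will have fewer cases. If placebo time is shorter, more cases are needed before the test can reject: at 264/308 with placebo time at 75%, 26 instead of 20.

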5.1.1.3 Primary Immunogenicity Hypotheses

No hypotheses will be tested.

5.1.1.4 Statistical Methods for Primary Immunogenicity Objective

The primary endpoints for the evaluation of immunogenicity are based on pseudovirus neutralizing antibody titers against D614 variant, which will be measured with the pseudovirus neutralization assay. The statistical analyses will be performed for the following primary endpoints below in each age and intervention group:

1. Neutralizing antibody titer on D01, D22, and D36
2. Fold-rise (fold-rise in serum antibody neutralization titer post-vaccination relative to D01) at D22, and D36
3. 2-fold and 4-fold rise in serum neutralization titer relative to D01 at D22, and D36
4. Occurrence of neutralizing antibody seroconversion, defined as baseline values below LLOQ with detectable neutralization titer above assay LLOQ at D22 and D36

The 95% CIs for the geometric mean titers (GMTs)/geometric mean concentrations (GMCs) and GMT ratios will be calculated using normal approximation of log-transformed titers. The 95% CIs for the proportions will be based on the Clopper-Pearson method. Additional parameters may be displayed as appropriate.

For descriptive purposes, the statistics presented in [Table 5.1](#) will be produced for each intervention group and each age group. The same dose-level group in Sentinel Cohort and Cohort 2 will be pooled for analysis.

Additionally, to evaluate independent determinants of primary immunogenicity endpoints, regression models may be constructed for log transformed titers and occurrence of 4-fold rise in serum neutralization titer relative to D01 at D22 for Cohort 1 and D36 for Sentinel Cohort and Cohort 2. When the outcome/dependent variable is a continuous numerical variable, linear model may be utilized; when the outcome/dependent variable is a categorical variable, logistic regression models may be utilized. Explanatory/independent variables inserted in these models would include age group (18-49 years, ≥ 50 years) and the injection schedule (1-injection, 2-injections). Models evaluating antibody titers or rates may include also an explanatory variable corresponding to the antigen dose level (ultra-low-dose, low-dose, medium-dose) when more than 1 dose level is to be used for the Full enrollment Cohort. Multiplicative interaction terms will be included in expanded models to assess for evidence of effect modification. Non-significant interaction terms with critical value < 0.05 can be removed from the models.

As the development of the mRNA COVID-19 vaccine has been suspended, the between groups ratios of GMTs and seroconversion rates differences planned at the time of the protocol will not be performed.

5.1.2 Hypotheses and Statistical Methods for Secondary Objectives

5.1.2.1 Secondary Immunogenicity Hypotheses

No hypotheses were tested.

5.1.2.2 Statistical Methods for Secondary Immunogenicity Objectives

The secondary endpoints for the evaluation of immunogenicity are presented in Table 3.1 of the protocol. The 95% CIs for the anti-S antibody concentration and anti-S antibody concentration ratio will be calculated using normal approximation of log-transformed titers. The 95% CIs for the proportions will be based on the Clopper-Pearson method. Additional parameters may be displayed as appropriate.

For descriptive purposes, the statistics presented in [Table 5.1](#) will be produced.

As the development of the mRNA COVID-19 vaccine has been suspended, the between groups ratios of anti-S antibody concentrations and seroconversion rates differences planned at the time of the protocol will not be performed.

Handling unscheduled serology samples

As scheduled visits after D22 or D36 were no longer required after enrollment and vaccination was interrupted, it is expected that a very limited number of serology samples will be within the planned time window at D91 (Cohort 1) or D112 (Sentinel Cohort and Cohort 2), D181 (Cohort 1) or D202 (Sentinel Cohort and Cohort 2), and D366 (Cohort 1) or D387 (Sentinel Cohort and Cohort 2). Nevertheless, a number of serology samples were obtained at unscheduled visits from participants prior to receipt of an authorized/approved COVID-19 vaccine or unblinding. To

assess the long-term immunogenicity, the unscheduled visit from each participant will need to be associated with one of the protocol-defined schedule visit, based on the rules detailed in [Table 5.2](#).

Table 5.2: Derivation rules to map unscheduled visits to protocol-defined visits

Injection scheme	Analysis visit	Protocol-defined timelines	Derivation rule for unscheduled visits
1 injection	V02	D09 (V01+8 days) [+2 days]	$1 \leq \text{Unscheduled visit date} - \text{V01 date} \leq 15$
	V03	D22 (V01+21 days) [+7 days]	$16 \leq \text{Unscheduled visit date} - \text{V01 date} \leq 31$
	V04	D36 (V01+35 days) [+7 days]	$32 \leq \text{Unscheduled visit date} - \text{V01 date} \leq 66$
	V05	D91 (V01+90 days) [+7 days]	$67 \leq \text{Unscheduled visit date} - \text{V01 date} \leq 138$
	V06	D181 (V01+180 days) [+14 days]	$139 \leq \text{Unscheduled visit date} - \text{V01 date} \leq 279$
	V07	D366 (V01+365 days) [+14 days]	$280 \leq \text{Unscheduled visit date} - \text{V01 date}$
2 Injections	V04	D30 (V03+8 days) [+2 days]	$1 \leq \text{Unscheduled visit date} - \text{V03 date} \leq 12$
	V05	D36 (V03+14 days) [+7 days]	$13 \leq \text{Unscheduled visit date} - \text{V03 date} \leq 55$
	V06	D112 (V03+90 days) [+7 days]	$56 \leq \text{Unscheduled visit date} - \text{V03 date} \leq 138$
	V07	D202 (V03+180 days) [+14 days]	$139 \leq \text{Unscheduled visit date} - \text{V03 date} \leq 279$
	V08	D387 (V03+365 days) [+14 days]	$280 \leq \text{Unscheduled visit date} - \text{V03 date}$

5.1.2.3 Secondary Efficacy Hypotheses

No hypotheses were tested.

